6.6 Management of Device Failure

If there is a device malfunction during the initial endoscopic placement (e.g. balloon is deflated, perforated, or other failure), then the balloon will be replaced with a new balloon during the same procedure.

During the follow-up visits or phone calls, if there is concern that the balloon is malfunctioning or may be deflated after successful placement, which can be suggested by the lack of satiety, ability to eat larger meals, or failure to lose weight during two consecutive follow-up visits, an abdominal ultrasound assessment will be performed.

- If the balloon is intact, then no endoscopic assessment will be indicated.
- If there is evidence of balloon malfunction without complication, a new balloon will be placed.
- If the balloon is deflated in the stomach, it will be replaced endoscopically with a new balloon.
- If the balloon is not in the stomach and subject has no symptoms of small bowel obstruction, the subject will be observed for 3 days for spontaneous passage of the balloon. Serial abdominal x-rays will be performed to monitor progression of the balloon in addition to clinical follow-up of signs and symptoms that may indicate a small bowel obstruction (e.g. pain, bilious vomiting, etc.) If the balloon doesn't pass, an attempt to remove it endoscopically will be performed. If not reachable by the endoscopy, the subject will be referred for surgical removal.

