The multidisciplinary team consisting of a pediatric endocrinologist or pediatric gastroenterologist, and a dietitian at the weight management clinic, will evaluate the patient at baseline, at 3 and 6 months after the insertion of the balloon, and at 9 and 12 months, which would be after the removal of the balloon. The dietitian at the weight management clinic will review the PN Q and the food record template and guide the diet modification accordingly. Subjects will have follow up psychology visits to support adherence and address any emotional and social adjustment concerns. Blood and urine samples will also be collected at months 3, 6, 9 and 12, after the IGB insertion. The subjects and their parents will be contacted by phone by a GI nurse to answer telephone questionnaire in between the visits on site at 4 days, 2 weeks, and at months 1, 2, 4, 5, 7, 8, 10, and 11, after the IGB insertion.

Blood Samples: Eight to twelve hour fasting blood samples will be collected at baseline, 3, 6, 9, and 12 month visits including:

- CBC with differential
- Electrolytes panel (Sodium, Potassium, Calcium, Creatinine, Chloride, Bicarbonate, BUN)
- Liver function tests (AST, ALT, Alkaline phosphatase, Total Bilirubin, Total Protein, Albumin)
- Nutritional assessment (Fe/TIBC, B12, Folic Acid, 25-Hydroxy Vitamin D, Ferritin)
- Coagulation panel (ProTime/INR, PTT)
- Total Cholesterol/Lipid panel
- Thyroid function tests, PTH
- Insulin
- Glucose
- CRP
- HgA1c

The effect of the IGB on the GI physiology will be assessed by collecting the following GI hormones at baseline and at 3, 6, 9 and 12 months: Total Ghrelin; PYY; GLP-1; and Leptin.

In total, approximately 40 ml of blood will be drawn for all blood tests.

Urine Sample: A urine sample will be collected at baseline, 3, 6, 9, and 12 months.

Stool Sample: A stool sample will be collected for a fecal antigen study for Helicobacter pylori (H. pylori) (sensitivity > 96.8%) to exclude the presence of H. pylori prior to the initial endoscopic assessment.

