5.4 Subject Compliance Monitoring

The Orbera IGB will be advanced to the stomach under endoscopy guidance and inflated with approximately 600 ml of normal saline. Subject transient nausea and pain symptoms will be managed with few days course of antiemetic and antispasmodics as per our clinical practice. Subject and their parents will then receive a phone call by a GI nurse at 4 days after the procedure (\pm 1 day), then 2 weeks (\pm 1 week), at 1 month (\pm 1 week), and monthly thereafter (\pm 1 week) when not being seen for a physical exam and in the weight management clinic at months 3, 6, 9, and 12 (\pm 1 week), per the clinical protocol visit schedule for the IGB as indicated on Table 2. The PI will evaluate all subjects if the GI nurse feels they need to be evaluated based on results of telephone questionnaire.

At 6 months (\pm 1 week), the subject will return for balloon removal at the pediatric endoscopy unit under monitored pediatric anesthesia care. During this visit, the subject will have blood samples drawn; a physical exam by pediatric gastroenterologist ([name]) or pediatric endocrinologist ([name]), followed by a meeting in the weight management clinic with the dietitian. Following the blood samples, PE, and WMC, the balloon will be removed at the same visit using the standard balloon retrieval kit approved by the FDA.

After balloon removal, all subjects will continue to be followed by the weight management team as indicated on Table 2. Weight, height, waist circumference, and demographic information will be collected at baseline, 3 months (\pm 1 week), time of balloon removal (6 months \pm 1 week), 9 months (\pm 1 week), and at 12 months (\pm 1 week).

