4-Female subjects will have a urine pregnancy test in the morning before the IGB insertion. Once the pregnancy test is confirmed negative, then the IGB can be inserted. At this visit, the subject will also be given a wallet card with emergency information, as well as Mayo Clinic brochures regarding the upper endoscopy and intragastric balloon for weight loss.

5-At the 6 month visit, the subject will have blood samples drawn; a physical exam by the pediatric endocrinologist ([name]) or a pediatric gastroenterologist ([name]); and a meeting in the weight management clinic with the dietitian. Following the blood samples, PE, and WMC, the IGB will be removed at the same visit. The 6 month visit and balloon removal may all be completed in one day, or they may be completed on separate days depending on scheduling times and the subject's availability. This will be up to the discretion of the study team. In order to prepare for the IGB removal, the subject will need to be on a liquid diet for 48 hours prior to its removal, and consume nothing by mouth for at least 12 hours prior to the IGB removal.

6-Other tests include:

- CBC with differential
- Electrolytes panel (Sodium, Potassium, Calcium, Creatinine, Chloride, Bicarbonate, BUN)
- Liver function tests (AST, ALT, Alkaline phosphatase, Total Bilirubin, Total Protein, Albumin)
- Nutritional assessment (Fe/TIBC, B12, Folic Acid, 25-Hydroxy Vitamin D, Ferritin)
- Coagulation panel (ProTime/INR, PTT)
- Total Cholesterol/Lipid panel

- Thyroid function tests, PTH
- Insulin
- Glucose
- CRP
- HgA1c
- Urine sample

7-Questionnaires will be given to the subject after consenting to complete at home with a request that they be returned at the baseline visit. The PN Q will be returned to and reviewed by the dietitian at the weight management clinic. The CES-D and SCAS will be returned to and reviewed by the psychologist during the subject's psychological assessment. Any elevations in the CES-D and SCAS surveys will be further assessed during the subject's visit with the psychologist. If clinically indicated, additional psychological assessment and follow-up that may be needed and will be part of the subject's standard of care.

8-At the PE, the subject's height, weight, waist circumference, HR, BP, and demographics will be collected at baseline, 3, 6, 9 , and 12 months.

7 Statistical Plan

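### On scheduled weights, the weight-loss sign of balloon deflation in section 6.6 cannot be met before the month-6 removal visit

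*Combined protocol and SAP*

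**What the plan says.** Section 6.6 sets out how a suspected device failure after placement is picked up. It opens with "During the follow-up visits or phone calls, if there is concern that the balloon is malfunctioning" or may have deflated. It then gives three signs that can suggest this: lack of satiety, being able to eat larger meals, and "failure to lose weight during two consecutive follow-up visits". An ultrasound of the abdomen then follows. If the ultrasound shows a malfunction without complication, or a balloon deflated in the stomach, 6.6 provides for a new balloon.

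The weight schedule is stated twice, and the two statements agree. Section 5.4 begins its list with "Weight, height, waist circumference, and demographic information will be collected at baseline, 3 months" and continues with balloon removal at 6 months, then 9 and 12 months, each with a window of one week either side. Footnote 8 of Table 2 says that "height, weight, waist circumference, HR, BP, and demographics will be collected at baseline, 3, 6, 9 , and 12 months".

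Between on-site visits, contact is by telephone. Section 3.1 has a GI nurse call subjects and parents "at 4 days, 2 weeks, and at months 1, 2, 4, 5, 7, 8, 10, and 11, after the IGB insertion", and 5.4 confirms that calls take place "when not being seen for a physical exam and in the weight management clinic at months 3, 6, 9, and 12". No section says that weight is obtained on a call. Under 5.4 and 6.7 the balloon comes out at 6 months, after that visit's physical exam.

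**The concern.** A criterion that needs two consecutive follow-up visits can work only if two such visits, with weights, fall early enough in the period it is meant to monitor. Here the implantation period is 6 months and the on-site visits are three months apart.

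Balloon deflation rates are a primary safety endpoint (3.4), and deflation resulting in small bowel obstruction is a stopping event (8.5). Table 2 has no row for routine abdominal imaging, so an ultrasound depends on the signs in 6.6 or on persistent symptoms under 6.2. Of the three signs in 6.6, weight is the only one that is measured; satiety and meal size rely on what an adolescent reports. If the measured sign matures only at removal, a subject who loses no weight but reports no change in appetite has no scheduled measurement that meets the criterion while the balloon is in place. The replacement that 6.6 provides for would also come too late to serve its purpose, since 3.1 insists on removal at 6 months.

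**Working it through.** The plan gives no figure to reproduce. The check is schedule arithmetic.

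**Inputs**
- Criterion: no weight loss during two consecutive follow-up visits (6.6).
- Follow-up weights: months 3, 6, 9 and 12, each ± 1 week (5.4; Table 2 footnote 8).
- Removal: month 6 ± 1 week (5.4), after the physical exam. Visit and removal may be on separate days (Table 2 footnote 5).
- Calls before removal: 4 days, 2 weeks, months 1, 2, 4 and 5, six in all (3.1).
- Conversion: 1 month = 365.25 / 12 / 7 = 4.348 weeks.

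**Step 1. When the weights fall**

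| Follow-up weight | Nominal week | Window (weeks) | Balloon |
|---|---|---|---|
| First, month 3 | 3 × 4.348 = 13.0 | 12.0 to 14.0 | in place |
| Second, month 6 | 6 × 4.348 = 26.1 | 25.1 to 27.1 | removal visit |
| Third and fourth, months 9 and 12 | after removal | – | out |

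Only one scheduled follow-up weight comes before the removal visit. The second consecutive one is the removal visit itself.

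**Step 2. Greatest possible lead time**
- Visit and removal on the same day: a matter of hours.
- Visit at the earliest date and removal at the latest: 27.1 − 25.1 = 2.0 weeks.
- So the criterion is unavailable for at least 25.1 / 27.1 = 93% of implantation, even in this most favourable case.

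**Step 3. Other readings of the criterion**
- *One interval between two follow-up visits.* The first such interval runs from month 3 to month 6, so the answer is still month 6.
- *Baseline as the first visit.* Baseline precedes insertion and is not a follow-up visit, so it does not bring the criterion forward.
- *Calls as visits.* Table 2 appears to number the calls as visits. On that reading the second contact would be at 2 weeks, but a weight would be needed that no section says is collected. Section 6.6 also separates follow-up visits from phone calls.
- *Extra physical exams.* The physical-exam row of Table 2 carries more marks than months 3, 6, 9 and 12, but in the text available its columns do not line up: the removal mark, for example, falls beside the label for Visit 7, which is paired with month 5. I have not relied on that row. Section 5.4 and footnote 8 are clear and agree.

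**The case against.** The strongest reply is that 6.6 does not make the weight sign a binding rule. The ultrasound follows from concern about the balloon, "which can be suggested by the lack of satiety, ability to eat larger meals, or failure to lose weight" and so on. The signs are permissive and joined by an alternative, so nothing stops the team acting on one poor weight at month 3.

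Other routes also stay open throughout. Satiety and meal size can come up at the month-3 visit or on any of the six calls. The investigator evaluates subjects whom the nurse flags (5.4). Section 6.2 provides an ultrasound when symptoms persist despite treatment and diet. Adverse events are asked about at every contact (8.2). Unscheduled weights are possible, and since the telephone questionnaire is not reproduced, it may already ask for weight.

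On scale, the pooled migration incidence quoted in 1.4 is 1.4%, giving 12 × 0.014 = 0.17 expected migrations if it applied to these 12 adolescents. That application is an assumption, and migration is not deflation. The number of detections that would be late because of this one sign is not quantified.

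Most of this stands. A reader might infer that deflation cannot be detected until removal, or that the 6.6 process as a whole cannot act. The documents do not support either, for the reasons just given. What the reply does not remove is the mismatch itself: 6.6 states a specific weight criterion that the stated weight schedule cannot satisfy in time. Permissive wording and a possible off-schedule weight reduce the consequence without making the criterion workable.

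**Conclusion.** The point holds as an inconsistency between 6.6 and the weight schedule. On scheduled weights, the one measured sign of deflation cannot be met before the month-6 removal visit in any of the 12 subjects, and it precedes removal by at most about two weeks.

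The practical consequence is limited to a deflation in a subject who reports no change in satiety or meal size and no persistent symptoms. Such a deflation could go unrecognised until removal. How often that would happen cannot be estimated from the documents. The primary weight-loss endpoint and its analysis are not affected.

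The conclusion assumes that follow-up visits means on-site visits after insertion, that weights are taken only when 5.4 and footnote 8 say, and that calls collect no weight. If the telephone questionnaire already records weight and calls are meant to count as visits, the criterion could be evaluated earlier; the protocol would then need to say so.

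**What to change.** Reconcile 6.6 with 5.4 and Table 2 so that the weight criterion can be evaluated while the balloon is in place. The text should make clear which contacts count as follow-up visits and which weights feed the criterion. How the clinical trigger should read is for the study clinicians.

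On the data side, check the telephone questionnaire. If it does not already ask for weight, add a self-reported home weight, recorded with its date, at the calls already scheduled at months 1, 2, 4 and 5.

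The cost is a wording change and one questionnaire item, with no added visit. The downside is that home weights are less precise than clinic weights. They should be flagged as self-reported in the database and not used for the primary endpoint.

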6.7 Removal of Balloon after 6 months by PI or Co-PI

The balloon will remain in the stomach if tolerated for 6 months, and then it will be removed endoscopically by a gastroenterologist ([name] or [name]). In order to prepare for the IGB removal, the subject will need to be on a liquid diet for 48 hours prior to its removal, and consume nothing by mouth for at least 12 hours prior to the IGB removal.

6.8 Schedule of Events

Table 2 provides a complete list of tests, procedures, and questions which will take place at each study visit, along with a time period and range for each study visit.

Table 2: Schedule of Events

Visit Type	Screening Visit	-4 weeks (+4 weeks)	-2 weeks (+2 weeks)	Day 0	Visit 0	4 days (± 1 day)	Visit 1	2 weeks (± 1 week)	Visit 2	1 month (± 1 week)	Visit 3	2 months (± 1 week)	Visit 4	3 months (± 1 week)	Visit 5	4 months (± 1 week)	Visit 6	5 months (± 1 week)	Visit 7	6 months (± 1 week)	Visit 8	7 months (± 1 week)	Visit 9	8 months (± 1 week)	Visit 10	9 months (± 1 week)	Visit 11	10 months (± 1 week)	Visit 12	11 months (± 1 week)	Visit 13	12 months (± 1 week)	Visit 14
Inclusion & Exclusion Criteria	x																																
Consent	x																																
Psychological exam		x													x					x									x				
Blood sample: GI hormones (2)		x												x				x		x					x			x			x		
Stool sample (3)		x												x																			
Urine pregnancy test (females) (4)				x																													
EGD/IGB insertion (1,4)				x																													
EGD/IGB removal (1,5)																			x														
Other Blood & Urine samples (6)		x												x				x		x					x			x			x		
PN Q (7)	x																														x		
CES-D & SCAS (7)	x													x																	x		
WMC		x												x				x		x					x			x			x		
PE (8)		x	x			x	x	x	x		x		x		x		x	x	x	x	x	x	x	x		x	x	x	x				
GI nurse telephone questionnaire					x	x	x	x	x	x	x	x	x	x	x	x	x	x	x	x	x	x	x	x	x	x	x	x	x				

Key:

EGD: upper endoscopy

IGB: Intragastric Balloon

PN Q: Pediatric Nutrition Questionnaire

CES-D: Self-Report Depression Scale Questionnaire

SCAS: Spence Child Anxiety Scale Questionnaire

WMC: Weight Management Clinic visit with dietitian

PE: Physical Exam by pediatric endocrinologist or pediatric gastroenterologist

Footnotes:

1-The IGB will be provided at no cost by the manufacturer.

2-GI hormones include: Total Ghrelin; PYY; GLP-1; and Leptin.

3-A stool sample will be collected for a fecal antigen study for H. pylori (sensitivity > 96.8%) to exclude the presence of H. pylori prior to the initial endoscopic assessment.

4-Female subjects will have a urine pregnancy test in the morning before the IGB insertion. Once the pregnancy test is confirmed negative, then the IGB can be inserted. At this visit, the subject will also be given a wallet card with emergency information, as well as Mayo Clinic brochures regarding the upper endoscopy and intragastric balloon for weight loss.

5-At the 6 month visit, the subject will have blood samples drawn; a physical exam by the pediatric endocrinologist ([name]) or a pediatric gastroenterologist ([name]); and a meeting in the weight management clinic with the dietitian. Following the blood samples, PE, and WMC, the IGB will be removed at the same visit. The 6 month visit and balloon removal may all be completed in one day, or they may be completed on separate days depending on scheduling times and the subject's availability. This will be up to the discretion of the study team. In order to prepare for the IGB removal, the subject will need to be on a liquid diet for 48 hours prior to its removal, and consume nothing by mouth for at least 12 hours prior to the IGB removal.

6-Other tests include:

- CBC with differential
- Electrolytes panel (Sodium, Potassium, Calcium, Creatinine, Chloride, Bicarbonate, BUN)
- Liver function tests (AST, ALT, Alkaline phosphatase, Total Bilirubin, Total Protein, Albumin)
- Nutritional assessment (Fe/TIBC, B12, Folic Acid, 25-Hydroxy Vitamin D, Ferritin)
- Coagulation panel (ProTime/INR, PTT)
- Total Cholesterol/Lipid panel

- Thyroid function tests, PTH
- Insulin
- Glucose
- CRP
- HgA1c
- Urine sample

7-Questionnaires will be given to the subject after consenting to complete at home with a request that they be returned at the baseline visit. The PN Q will be returned to and reviewed by the dietitian at the weight management clinic. The CES-D and SCAS will be returned to and reviewed by the psychologist during the subject's psychological assessment. Any elevations in the CES-D and SCAS surveys will be further assessed during the subject's visit with the psychologist. If clinically indicated, additional psychological assessment and follow-up that may be needed and will be part of the subject's standard of care.

8-At the PE, the subject's height, weight, waist circumference, HR, BP, and demographics will be collected at baseline, 3, 6, 9 , and 12 months.

7 Statistical Plan

This is a pilot study of 12 subjects only, so results will be largely descriptive. Standard statistical analysis will be performed. We will use t-tests or alternative measures will be used to test whether weight loss was significant from baseline to each of the follow up points.

8 Safety and Adverse Events

All adverse events occurring during the study, including those not meeting the criteria of an Unanticipated Adverse Device Effect (UADE) will be recorded on the appropriate case report form. Records of these events will be maintained and reports submitted to the FDA and IRB according to the regulatory requirements. All adverse events will be reported. Expected clinical adverse events and anticipated adverse device effects are those listed in Section 1.5.2.

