6.3 Indications for Follow-up Endoscopy

After the balloon is inserted, an endoscopy will be required if:

- persistent abdominal pain
- GERD symptoms
- evidence of GI bleeding
- evidence of new microcytic anemia
- balloon deflation on abdominal ultrasound or x-ray

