- If pancreas enzymes are $> 3X$ upper limit of normal for institution,
 - In a systemically ill patient with evidence of severe acute pancreatitis (requiring > 3 days hospitalization, OR evidence of end organ damage [acute renal failure, respiratory distress, or meeting SIRS (systemic inflammatory response syndrome) criteria for sepsis], OR cross sectional imaging suggestive of severe acute pancreatitis [evidence of pancreas necrosis or new pseudocyst], the balloon will be removed and close clinical follow-up of these severely ill patients will be required.
 - In a patient who does not meet the criteria of severe pancreatitis, pancreas enzymes will be repeated in 48 hours with clinical follow-up.
- If pancreas enzymes are $< 3X$ upper limit of normal for institution,
 - In a systemically ill patient with evidence of severe acute pancreatitis (requiring > 3 days hospitalization, OR evidence of end organ damage [acute

renal failure, respiratory distress, or meeting SIRS (systemic inflammatory response syndrome) criteria for sepsis], OR cross sectional imaging suggestive of severe acute pancreatitis [evidence of pancreas necrosis or new pseudocyst], the balloon will be removed and close clinical follow-up of these severely ill patients will be required.

- If typical pain persists for > 48-72 hours, pancreas enzymes will be repeated in 48 hours with clinical follow-up.
- If pain resolves within 48-72 hours, clinical follow-up will be required.

In addition to the above mentioned endoscopic findings, the balloon would be removed in case of:

- severe anticipated or unanticipated adverse events
- pregnancy
- subject and family request for balloon removal
- risk of continuation of the trial, in the opinion of the PI, due to psychosocial circumstances, noncompliance with the required follow-ups and removal, or if the subject is moving and there is a risk of not being able to remove the balloon at 6 months.

Otherwise, the balloon will stay in place and the subject will be treated symptomatically, as described in Section 6.2.

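### Pregnancy requires balloon removal, but the only pregnancy test the protocol requires is on the morning of insertion, so no required test would reveal an unrecognised pregnancy afterwards

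*Combined protocol and SAP*

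**What the plan says.** Section 4.2 (item 1) excludes pregnant subjects. Section 6.4 includes pregnancy in the list that begins "In addition to the above mentioned endoscopic findings, the balloon would be removed in case of".

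Testing is described in Sections 3.1 and 4.3 and in Table 2 with its footnote 4. All of them place it on the day of insertion: "Female subjects will have a urine pregnancy test in the morning before the IGB insertion". Footnote 4 makes the result a condition of placement: "Once the pregnancy test is confirmed negative, then the IGB can be inserted". The pregnancy-test row of Table 2 has one mark, on Day 0, and Section 6.8 presents the table as exhaustive: "Table 2 provides a complete list of tests, procedures, and questions which will take place at each study visit". The source map in Section 9.3 files the result with the eligibility data.

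After insertion, four things bear on pregnancy:

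- Female subjects agree to abstain or use contraception for a year (Section 4.1 item 4, Appendix A).
- Adverse events are sought by specific questioning at each contact, with examination as appropriate (Section 8.2).
- A nurse telephones between visits, and the investigator sees any subject about whom the nurse is concerned (Section 5.4).
- A subject who becomes sexually active during the trial must discuss contraception with her primary care provider (Appendix A).

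Urine is collected at months 3, 6, 9 and 12 (Section 3.1), with no assay named. Sections 6.2, 6.3, 6.6 and 6.7 mention no pregnancy test.

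**The concern.** The removal rule in Section 6.4 can act only on a pregnancy that someone has found. The protocol tests once, before the exposure starts, and then relies on a subject aged 14 to 17 knowing and reporting, or on a clinician thinking of it.

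Two later points matter most. First, continuing nausea and vomiting is a listed balloon risk (Section 1.5.2), so early pregnancy could be mistaken for a balloon effect. Section 6.2 deals with persistent symptoms by looking at diet, then at the balloon by ultrasound, and never at pregnancy. Second, Section 6.6 provides for a new balloon during the study ("If the balloon is deflated in the stomach, it will be replaced endoscopically with a new balloon"; "If there is evidence of balloon malfunction without complication, a new balloon will be placed") without repeating the test that was required for the first one. What is at stake is avoidable time with the balloon in place during a pregnancy, or a new placement in a subject whose pregnancy nobody has recognised.

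**Working it through.** The protocol gives no figure to reproduce. The check is a comparison of rules and a count of weeks and tests.

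**Inputs.** Visits at months 3 and 6, each ±1 week (Section 5.4, Table 2). Twelve subjects (Section 7). Telephone contacts at day 4, week 2 and months 1, 2, 4 and 5, and an on-site visit at month 3 (Section 3.1). Conversion assumed here: 3 months = 13 weeks and 6 months = 26 weeks.

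**Untested time with the balloon, as planned**

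- Removal at 26 ± 1 = 25 to 27 weeks, and the only test is at week 0.
- Untested exposure = 25 to 27 weeks.
- Contacts before month 6: day 4, week 2, months 1, 2, 3, 4, 5 = 7, none with a test.

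**With a month-3 test**

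- Month 3 = 13 ± 1 = 12 to 14 weeks.
- Day 0 to month 3: 12 to 14 weeks.
- Month 3 to removal: 25 − 14 = 11 weeks up to 27 − 12 = 15 weeks.
- Longest untested interval: at most 15 weeks.

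**Gain in time to removal.** A pregnancy detectable at month 3 and not otherwise recognised would lead to removal 11 to 15 weeks before the scheduled date. A later conception, or one already recognised, gains 0 weeks from this test. The range is therefore 0 to 15 weeks, and the top is a ceiling.

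**Rule against test, point by point**

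| Point in the plan | Rule on pregnancy | Test required |
|---|---|---|
| First balloon (footnote 4) | Excluded | Yes, same day |
| Month 3 visit | Remove if pregnant (6.4) | None |
| Persistent symptoms (6.2) | Remove if pregnant (6.4) | None |
| Follow-up endoscopy (6.3) | Remove if pregnant (6.4) | None |
| Replacement balloon (6.6) | Barred if known (5.3 with 4.2; 6.4) | None stated |
| Scheduled removal (6.7) | Removed in any case | None |

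The rule is present in every row where it matters. Only the first row has a required means of applying it.

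**Test count.** Month 3: 1 × 12 = 12 at most, if all subjects are female. Event-triggered tests cannot be counted from the documents. As an illustration, one symptom-triggered test in every subject would add another 12. The pooled 33.7% in Section 1.5.2 does not help, because it covers any pain or nausea rather than persistent nausea or vomiting.

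**The case against.** The strongest reply is that the plan already covers most of this.

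**Replacement balloons.** A reader might infer that Section 6.6 allows a new balloon in a pregnant subject and so contradicts Section 6.4. The documents do not support that. Section 5.3 restricts use of the balloon to adolescents who meet the criteria in Sections 4.1 and 4.2, which exclude pregnancy, and Section 6.4 orders removal. Footnote 4 is attached to the insertion row and could even be read as covering any insertion, although its other content (such as the wallet card) points to Day 0. What stands is that no repeat test is stated.

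**Follow-up endoscopy.** A reader might also infer that after an endoscopy ("After the balloon is inserted, an endoscopy will be required if") with no removal finding, an unrecognised pregnancy simply continues with the balloon. But Section 6.4 sends the subject back: "Otherwise, the balloon will stay in place and the subject will be treated symptomatically, as described in Section 6.2". Section 6.2 ends in removal for intolerance if symptoms persist with an intact balloon. Nausea and vomiting are also not among the five indications in Section 6.3. Continued exposure follows only if symptoms settle or the Section 6.2 steps are not completed. A test would shorten that path; it is not the only way out of it.

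**Removal day.** A positive test there does not change the removal. It would only inform the anesthesia team, and local pre-anesthesia screening is not described either way.

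**Unseen material.** The telephone questionnaire may ask about pregnancy, and clinicians may test on their own judgment. Neither can be confirmed or ruled out, so it would be wrong to say that nobody asks. It remains true that the protocol requires no test. A pregnancy assay on the later urine samples is unlikely to be intended, since the test has its own row in Table 2.

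**Size of the risk.** There are 12 subjects, under contraception agreements, and Section 1.5.2 lists no balloon harm specific to pregnancy. The week counts describe the schedule, not a risk.

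**Conclusion.** The point holds as a gap in detection. A stated safety rule has no required test behind it for the 25 to 27 weeks it is meant to operate, including before a replacement balloon. It does not show that the plan permits a balloon in a subject known to be pregnant, or that an unrecognised pregnancy would necessarily run to month 6.

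The measurable benefit of the scheduled part of the fix is a longest untested interval of at most 15 weeks and a gain in time to removal of 0 to 15 weeks. Both rest on 13-week and 26-week visits kept within ±1 week, and the gain also requires a pregnancy detectable by month 3 and not otherwise recognised. No probability of pregnancy is given, so no expected number of cases is offered.

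This concerns safety monitoring, not the statistical analysis. It is a minor change to the safety schedule, worth making because it is cheap.

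**What to change.** 1. **Table 2, pregnancy-test row:** add a mark at month 3, run on the urine already collected at that visit.
2. **Section 6.2:** in female subjects whose nausea or vomiting persists after 1 to 2 weeks of treatment, do a urine pregnancy test before attributing symptoms to diet or to balloon intolerance.
3. **Footnote 4 and Section 6.6:** require a negative urine pregnancy test on the same day before any balloon placement, replacements included, and before a non-emergency follow-up endoscopy under Section 6.3. An emergency endoscopy is not delayed.
4. **Positive result with the balloon in place:** handle under Section 6.4, which needs no new rule.

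A test on the day of scheduled removal is optional, for the anesthesia team's information.

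**Cost:** one scheduled urine test per female subject still carrying the balloon at month 3, plus event-triggered tests, some of which need a fresh sample. No visit is added. The edits are one table row, one footnote and short additions to Sections 6.2 and 6.6, with a matching line in the consent form. Minors' results need confidential handling, as the Day 0 test already does.
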